## 8.6. Safety Analysis

All safety data collected on or after the date that study drug was first administered up to the date of last dose of study drug plus 30 days will be summarized by hepatic function group (according to the study drug received) using safety analysis set.

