## **4. SUBJECT DISPOSITION**

### **4.1. Subject Enrollment and Disposition**

A summary of subject enrollment and disposition will be provided by hepatic function group and by hepatic function group within cohort. This summary will present the number of subjects enrolled, and the number and percentage of subjects in each of the categories listed below. For the Safety Analysis Set category, the denominator for the percentage calculation will be the total number of subjects enrolled for each column. For all other categories, the denominator for the percentage calculation will be the total number of subjects in the Safety Analysis Set for each column.

- Safety Analysis Set
- PK Analysis Set for each analyte
- PD Analysis Set for each biomarker
- Completed study drug
- Did not complete study drug with reason for premature discontinuation of study drug
- Completed the study
- Did not complete the study with reason for premature discontinuation of study

In addition, the total number of subjects who were enrolled, and the number of subjects in each of the disposition categories listed above will be displayed in a flowchart.

The following by-subject listings will be provided by subject ID number in ascending order to support the above summary tables:

- Reasons for premature study drug or study discontinuation

A by-subject listing of subject disposition including cohort, hepatic function group, date of the last dose of study drug (study days), study drug completion status, reason for study drug discontinuation, study completion status, reason for study discontinuation, PK set status (indicating whether or not a subject is included in a PK analysis set), and PD set status will be provided by subject ID number in ascending order.

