## **5. BASELINE CHARACTERISTICS**

### **5.1. Demographics**

Subject demographic variables (ie, age, sex, race, and ethnicity) will be summarized by hepatic function group and by hepatic function group within cohort using descriptive statistics for age, and using numbers and percentages of subjects for sex, race, and ethnicity. The summary of demographic data will be provided for the Safety Analysis Set.

A by-subject demographic listing, including the informed consent date, will be provided by subject identification (ID) number in ascending order.

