## **7.1.7. Summaries of Adverse Events and Deaths**

Treatment-emergent AEs will be summarized based on the Safety Analysis Set.

The number and percentage of subjects who experienced at least 1 TEAE will be provided and summarized by SOC, PT, and hepatic function group as follows:

- All TEAEs
- TEAEs of Grade 3 or above
- TEAEs of Grade 2 or above
- All TEAEs by severity
- All TE treatment-related AEs

- All TE treatment-related AEs by severity
- All TEAEs related to study procedures
- All TE SAEs
- All TE treatment-related SAEs
- All TEAEs leading to premature discontinuation of study drug
- All TEAEs leading to premature discontinuation of study

A brief, high-level summary of AEs described above will be provided by hepatic function group and by the number and percentage of subjects who experienced the above AEs. All deaths observed in the study will also be included in this summary.

Multiple events will be counted only once per subject in each summary. Adverse events will be summarized and listed first in alphabetic order of SOC and then by PT in descending order of total frequency within each SOC. For summaries by severity, the maximum severity will be used for those AEs that occurred more than once in an individual subject during the study.

In addition, data listings will be provided for the following:

- All AEs, indicating whether the event is treatment emergent
- SAEs
- Deaths
- AEs leading to premature discontinuation of study drug
- AEs leading to discontinuation of study

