### **7.2.1. Summaries of Numeric Laboratory Results**

Descriptive statistics will be provided by hepatic function group for each laboratory test specified in the study protocol as follows:

- Predose values
- Values at each postdose visit
- Change from predose at each postdose visit

Predose and postdose values will be defined as described in Section 3.7.1. Change from predose to a postdose visit will be defined as the visit value minus the predose value. The mean, median, Q1, Q3, minimum, and maximum values will be displayed to the reported number of digits; SD values will be displayed to the reported number of digits plus 1.

In the case of multiple values in an analysis window, data will be selected for analysis as described in Section 3.7.3.

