#### 7.2.2.2. Summaries of Laboratory Abnormalities

Laboratory data that are categorical will be summarized using the number and percentage of subjects in the study with the given response at predose and each scheduled postdose visit.

The following summaries (number and percentage of subjects) for treatment-emergent laboratory abnormalities will be provided by lab test and hepatic function group; subjects will be categorized according to the most severe postdose abnormality grade for a given lab test:

- Graded laboratory abnormalities
- Grade 3 or 4 laboratory abnormalities

For all summaries of laboratory abnormalities, the denominator is the number of subjects with nonmissing postdose values up to 30 days after last dosing date.

A by-subject listing of treatment-emergent laboratory abnormalities will be provided by subject ID number and visit in chronological order. This listing will include all test results that were collected throughout the study for the lab test of interest, with all applicable severity grades displayed.

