#### 7.3. Vital Signs

Descriptive statistics will be provided by hepatic function group for vital signs as follows:

- Predose value
- Values at each postdose visit
- Change from predose at each postdose visit

Predose and postdose values will be defined as described in Section 3.7.1. Change from predose to a postdose visit will be defined as the postdose value minus the predose value.

In the case of multiple values in an analysis window, data will be selected for analysis as described in Section 3.7.3. No formal statistical testing is planned.

A by-subject listing of vital signs will be provided by subject ID number and visit in chronological order.

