#### **7.5. Investigator Electrocardiogram Assessment**

A shift table of the investigators' assessment of ECG results at each visit compared with predose values will be presented by hepatic function group using the following categories: normal; abnormal, not clinically significant; abnormal, clinically significant; or missing. The number and percentage of subjects in each cross-classification group of the shift table will be presented. Subjects with a missing value at predose or postdose will not be included in the denominator for percentage calculation. No formal statistical testing is planned.

A by-subject listing for ECG assessment results will be provided by subject ID number and visit in chronological order.

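### As written, the SAP safety tables pool 30 mg and 10 mg healthy controls into one normal group, so no impairment group has a normal column at its own dose alone

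*SAP*

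**What the plan says.** The Protocol Synopsis and SAP 1.3 give Cohorts 1 and 2 (mild, moderate) a single 30 mg dose and Cohort 3 (severe) a single 10 mg dose. Each cohort has 10 impaired subjects and 10 matched normal controls, so normal subjects are dosed at both levels.

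The safety sections of the SAP group the data as follows.
- 7.1.7, adverse events: counts of subjects "will be provided and summarized by SOC, PT, and hepatic function group as follows".
- 7.2.1, numeric laboratory results: "Descriptive statistics will be provided by hepatic function group for each laboratory test specified in the study protocol as follows".
- 7.2.2.2, laboratory abnormalities: summaries "for treatment-emergent laboratory abnormalities will be provided by lab test and hepatic function group".
- 7.3, vital signs: "Descriptive statistics will be provided by hepatic function group for vital signs as follows".
- 7.5, ECG: a shift table of results "compared with predose values will be presented by hepatic function group using the following categories".

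SAP 7.1.8 plans no further adverse event analysis. Other sections are more detailed. In 4.1, "A summary of subject enrollment and disposition will be provided by hepatic function group and by hepatic function group within cohort". In 5.1, demographic variables "will be summarized by hepatic function group and by hepatic function group within cohort using descriptive statistics for age"; 5.2 does the same for baseline characteristics. SAP 8 and 9 present PK and PD results by group within cohort.

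Protocol 8.6 says that safety data will be "summarized by hepatic function group (according to the study drug received) using safety analysis set".

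On reuse of controls, the Synopsis and SAP 1.3 let a normal subject serve more than one cohort only where the dose is the same. Protocol 3.1 permits reuse in another cohort and states no dose condition.

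**The concern.** Safety and tolerability in each hepatic function group is a secondary objective, and readers will naturally set each impaired column beside the normal column. If that column mixes two doses, a difference from it reflects impairment and dose together, and so can the absence of a difference. The sponsor chose the lower dose for severe impairment to protect exposure margins (Protocol 1.3.1), so dose is a feature that the safety tables should show. The mixing does not depend on any matching error: it occurs even when every control is matched at the correct dose.

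The missing condition in Protocol 3.1 is a separate and smaller matter of consistency between sections.

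**Working it through.** **The plan's own figure.** The sample size statement (Protocol 8.10, SAP 1.4) reproduces. With 8 per group, SD 0.463, true ratio 1.0, limit 2.0 and one-sided 5%, the noncentrality is ln 2 / (0.463 × √(2/8)) = 0.693/0.2315 = 2.99 on 14 df, and the probability is 0.885 against the stated 88% or more. The overage also agrees: 8 × 1.25 = 10 per group, × 6 groups = 60. Nothing below depends on these figures.

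**Make-up of the pooled normal group.** Let s be the number of controls shared between Cohorts 1 and 2, which is allowed because both use 30 mg. There are then 20 − s distinct controls at 30 mg and 10 at 10 mg. The share at 30 mg is w = (20 − s)/(30 − s).
- s = 0: 20/30 = 67% at 30 mg, 33% at 10 mg.
- s = 3: 17/27 = 63% and 37%.
- s = 4: 16/26 = 62% and 38%.
- s = 10: 10/20 = 50% and 50%.

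The values 3 and 4 are indicative. Table 1-3 of the protocol fills 4 × 10 = 40 places, while Section 1.2.5.2.1 reports 37 subjects enrolled by 1 November 2017. If the table has the same cut-off and all 37 subjects belong to Cohorts 1 and 2, at least 40 − 37 = 3 controls were used twice, or 4 if the discontinued subject is not in the table. The table states no cut-off, so the full range of 50% to 67% is the safe statement.

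**What pooling does to a side-by-side reading.** Suppose the adverse event risk in controls is d percentage points higher at 30 mg than at 10 mg. The pooled normal risk is the 10 mg risk plus w·d. Compared with a same-dose reference, the severe-minus-normal difference moves by −w·d, and the mild- or moderate-minus-normal difference moves by +(1 − w)·d.
- d = 0: no shift.
- d = 10 (assumed): severe −5.0 to −6.7 points; mild and moderate +3.3 to +5.0.
- d = 20 (assumed): severe −10.0 to −13.3 points; mild and moderate +6.7 to +10.0. For example, rates of 30% and 10% give a pooled rate of (10 × 30 + 10 × 10)/20 = 20% to (20 × 30 + 10 × 10)/30 = 23.3%.

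The only rates in the documents are those of GS-US-402-1851 (Protocol 1.2.5.1): 4/15 (27%) at 10 mg and 4/15 (27%) at 30 mg, so d = 0 as observed. That estimate is loose. Its standard error is √(2 × 0.267 × 0.733/15) = 0.161, giving a 95% interval of about ±32 points by the normal approximation. The 15 per cohort, against N = 12 in the PK table, may also include placebo subjects.

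**Precision of a split column.** With zero events in n subjects, the exact two-sided 95% upper limit is 1 − 0.025^(1/n): 31% for n = 10 and 13% for n = 27.

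**The case against.** Five points can be made for the plan.

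1. No passage says that there will be one normal column. SAP 1.3 describes two groups in each cohort, Protocol 8.6 refers to the study drug received, and SAP Table 8-1 lists the two doses as separate treatments. A split by dose is therefore a possible reading. This stands in part: the single column is an inference. However, SAP 4.1, 5.1 and 5.2 use the hepatic function group and the group within cohort as two different presentations, and Section 7 uses only the first. All controls receive GS-9674, and neither Protocol 8.6 nor Table 8-1 defines a dose split for safety.

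2. The safety objective names no contrast with controls, and no formal safety testing is planned. This stands. A reader might infer that the plan contains a biased severe-versus-normal safety estimate; it contains no such estimate, only descriptive columns.

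3. Same-dose controls are not plainly the better safety reference. Unbound parent exposure was more than 4-fold higher in moderate impairment (Protocol 1.2.5.3). If severe impairment is at least as marked, a severe subject on 10 mg would exceed even a 30 mg control, whose mean AUCinf was 2480/1260 = 1.97 times that at 10 mg (Table 1-2, fasted). A larger pooled group also gives a steadier background rate. This is a good reason to keep the pooled column, but not to omit the same-dose one, which separates impairment from dose.

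4. Dose can be traced, since the listings give cohort, exposure and all adverse events by subject. This stands and limits the consequence.

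5. The reuse wording is already settled by the Synopsis and SAP 1.3, and Protocol 3.1 itself plans 10 controls for Cohort 3. This stands.

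**Conclusion.** The point holds as a minor improvement to the presentation of safety data. Followed as written, the five SAP sections give the severe group a normal reference of which 50% to 67% took 30 mg, and the mild and moderate groups one of which 33% to 50% took 10 mg. This assumes 10 controls at 10 mg and between none and all ten controls shared between Cohorts 1 and 2.

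The effect on any safety result is unknown. It is zero if risk does not differ between 10 and 30 mg, as the observed Phase 1 rates suggest; the shifts for d = 10 and d = 20 are illustrations, not estimates. The planned tables could not show which case applies. No sample size, alpha, power or formal test is affected.

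A reader might also infer from Protocol 3.1 that 30 mg controls could enter the Cohort 3 PK comparison and pull the severe-to-normal ratio towards no effect. The documents do not support that as a defect of the analysis: the Synopsis and SAP 1.3 restrict reuse to the same dose, and under that rule each by-cohort PK comparison is at a single dose and needs no dose term. No PK bias is claimed.

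**What to change.** In SAP 7.1.7, 7.2.1, 7.2.2.2, 7.3 and 7.5, present the normal group by dose received (30 mg and 10 mg) and keep the pooled column. Alternatively, use the double presentation already specified in SAP 4.1, by group and by group within cohort. The split by dose is slightly simpler, because a control shared by Cohorts 1 and 2 is then counted once; within cohort, the same subject would appear under both cohorts and need a footnote.

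The cost is some added columns and no extra subjects or data, since the 10 mg controls are already planned. The drawback is precision: with about 10 subjects, an event seen in none of them is still compatible with a rate of up to 31%, which is why the pooled column should stay.

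As a consistency edit only, add the same-dose condition on control reuse to Protocol 3.1, to agree with the Synopsis and SAP 1.3.

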#### **7.1.8. Additional Analysis of Adverse Events**

No additional analysis of adverse events is planned.

#### **7.2. Laboratory Evaluations**

Laboratory data collected during the study will be analyzed and summarized using both quantitative and qualitative methods. Summaries of laboratory data will be provided for the Safety Analysis Set and will include data collected up to the last dose of study drug plus 30 days for subjects who have permanently discontinued study drug. The analysis will be based on values reported in conventional units. When values are BLQ, they will be listed as such, and the imputed value will be used for the purpose of calculating summary statistics. Hemolyzed test

results will not be included in the analysis, but they will be listed in by-subject laboratory listings.

A by-subject listing for laboratory test results will be provided by subject ID number and visit in chronological order for hematology, serum chemistry, and urinalysis separately. Values falling outside of the relevant reference range and/or having a severity grade of 1 or higher on the Gilead Grading Scale for Severity of Adverse Events and Laboratory Abnormalities will be flagged in the data listings, as appropriate.

No formal statistical testing is planned.

### **7.2.1. Summaries of Numeric Laboratory Results**

Descriptive statistics will be provided by hepatic function group for each laboratory test specified in the study protocol as follows:

- Predose values
- Values at each postdose visit
- Change from predose at each postdose visit

Predose and postdose values will be defined as described in Section 3.7.1. Change from predose to a postdose visit will be defined as the visit value minus the predose value. The mean, median, Q1, Q3, minimum, and maximum values will be displayed to the reported number of digits; SD values will be displayed to the reported number of digits plus 1.

In the case of multiple values in an analysis window, data will be selected for analysis as described in Section 3.7.3.

### **7.2.2. Graded Laboratory Values**

The Gilead Grading Scale for Severity of Adverse Events and Laboratory Abnormalities will be used to assign toxicity grades (0 to 4) to laboratory results for analysis. Grade 0 includes all values that do not meet the criteria for an abnormality of at least Grade 1. For laboratory tests with criteria for both increased and decreased levels, analyses for each direction (ie, increased, decreased) will be presented separately.

#### **7.2.2.1. Treatment-Emergent Laboratory Abnormalities**

Treatment-emergent laboratory abnormalities are defined as values that increase at least 1 toxicity grade from predose at any postdose visit, up to and including the date of last dose of study drug plus 30 days for subjects who permanently discontinued study drug. If the relevant predose laboratory value is missing, any abnormality of at least Grade 1 observed within the time frame specified above will be considered treatment emergent.

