#### **4.2.2. Subjects with Impaired Hepatic Function**

Subjects with mild, moderate, or severe hepatic impairment must also meet the following additional inclusion criteria to be eligible for participation in this study:

12. Aside from hepatic insufficiency, the subject must, in the opinion of the investigator, be sufficiently healthy for study participation based upon medical history, physical examination, vital signs, and screening laboratory evaluations
13. Must have diagnosis of chronic ( $> 6$  months), stable hepatic impairment with no clinically significant changes within 3 months (90 days) prior to study drug administration (Day -1)

14. Must meet all of the following laboratory parameters at Screening:

- ALT value  $\leq 10 \times$  ULN
- AST value  $\leq 10 \times$  ULN
- Absolute neutrophil count  $\geq 1,000/\text{mm}^3$
- Platelets  $\geq 25,000/\text{mm}^3$
- Hemoglobin  $\geq 8$  g/dL
- $\alpha$ -fetoprotein  $\leq 50$  ng/mL

15. Subjects with severe hepatic impairment must have a score on the Child Pugh Turcotte scale of 10-15 at Screening. If a subject's score changes during the course of the study, the score at Screening will be used for classification.

16. Subjects with moderate hepatic impairment must have a score on the Child Pugh Turcotte scale of 7-9 at Screening. If a subject's score changes during the course of the study, the score at Screening will be used for classification.

17. Subjects with mild hepatic impairment must have a score on the Child Pugh Turcotte scale of 5-6 at Screening. If a subject's score changes during the course of the study, the score at Screening will be used for classification.

18. Subjects with hepatic impairment with comorbid diseases not associated with hepatic impairment requiring medication(s) must be taking the medication(s) without a change in dose for at least 4 weeks (or 5 half-lives, whichever is longer) prior to Screening. Any change in the dosage during this timeframe should be reviewed and approved by the Sponsor.

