#### **7.5. Clinical Laboratory Abnormalities and Other Abnormal Assessments as Adverse Events or Serious Adverse Events**

Laboratory abnormalities are usually not recorded as AEs or SAEs. However, laboratory abnormalities (eg, clinical chemistry, hematology, and urinalysis) independent of the underlying medical condition that require medical or surgical intervention or lead to investigational medicinal product interruption or discontinuation must be recorded as an AE, as well as an SAE, if applicable. In addition, laboratory or other abnormal assessments (eg, ECG, X-rays, vital signs) that are associated with signs and/or symptoms must be recorded as an AE or SAE if they meet the definition of an AE (or SAE) as described in Sections 7.1.1 and 7.1.2. If the laboratory abnormality is part of a syndrome, record the syndrome or diagnosis (ie, anemia) not the laboratory result (ie, decreased hemoglobin).

Severity should be recorded and graded according to the Gilead Grading Scale for Severity of Adverse Events and Laboratory Abnormalities as described in [Appendix 4](#). The GSI Grading Scale for Severity of Adverse Events and Laboratory Abnormalities has been modified to be more appropriate for healthy volunteers and patients with inflammatory diseases (eg, rheumatoid arthritis, asthma, psoriasis). For AEs associated with laboratory abnormalities, the event should be graded on the basis of the clinical severity in the context of the underlying conditions; this may or may not be in agreement with the grading of the laboratory abnormality.

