## **7.7. Study Specific Stopping Criteria**

Study drug dosing of a cohort will be suspended and, based on full review of the clinical data by the MM and in discussion with the investigator, may be halted when:

- 2 healthy control subjects dosed with GS-9674 within a cohort experience elevations in liver function tests of ALT and/or AST > 5 x the upper limits of normal (ULN); or ALT > 3 x ULN and total bilirubin > 2 x ULN, confirmed by immediate repeat testing.
- 2 hepatic impairment subjects dosed with GS-9674 within a cohort experience elevation of baseline liver function tests of ALT and/or AST > 3 x baseline; or ALT > 2 x baseline and total bilirubin > 2 x baseline.
- 1 subject experiences a SAE possibly related to the study drug
- The sponsor unilaterally requests it.

Decisions to reinstate the study will be made in consultation with the sponsor and pending a safety review.

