#### **8.1.3. Secondary Endpoint**

The secondary endpoints are the incidences of AEs and laboratory abnormalities, physical examinations, vital signs, ECGs, and PD markers including but not limited to FGF19 and C4.

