Infant, < 7 Days	6.5 to 7.5 mg/dL 1.61 to 1.88 mmol/L	6.0 to < 6.5 mg/dL 1.49 to < 1.61 mmol/L	5.5 to < 6.0 mg/dL 1.36 to < 1.49 mmol/L	< 5.5 mg/dL < 1.36 mmol/L
Hypercalcemia (corrected for albumin if appropriate*) Adult and Pediatric ≥ 7 Days	>ULN to 11.5 mg/dL >ULN to 2.88 mmol/L	> 11.5 to 12.5 mg/dL > 2.88 to 3.13 mmol/L	> 12.5 to 13.5 mg/dL > 3.13 to 3.38 mmol/L	> 13.5 mg/dL > 3.38 mmol/L
Infant, < 7 Days	11.5 to 12.4 mg/dL 2.86 to 3.10 mmol/L	> 12.4 to 12.9 mg/dL > 3.10 to 3.23 mmol/L	> 12.9 to 13.5 mg/dL > 3.23 to 3.38 mmol/L	> 13.5 mg/dL > 3.38 mmol/L
Hypocalcemia (ionized)	3.0 mg/dL to < LLN 0.74 mmol/L to < LLN	2.5 to < 3.0 mg/dL 0.62 to < 0.74 mmol/L	2.0 to < 2.5 mg/dL 0.49 to < 0.62 mmol/L	< 2.0 mg/dL < 0.49 mmol/L
Hypercalcemia (ionized)	> ULN to 6.0 mg/dL > ULN to 1.50 mmol/L	> 6.0 to 6.5 mg/dL > 1.50 to 1.63 mmol/L	> 6.5 to 7.0 mg/dL > 1.63 to 1.75 mmol/L	> 7.0 mg/dL > 1.75 mmol/L

CHEMISTRY				
	Grade 1	Grade 2	Grade 3	Grade 4
Hypomagnesemia	1.40 to <LLN mg/dL 1.2 to <LLN mEq/L 0.58 to <LLN mmol/L	1.04 to < 1.40 mg/dL 0.9 to < 1.2 mEq/L 0.43 to < 0.58 mmol/L	0.67 to < 1.04 mg/dL 0.6 to < 0.9 mEq/L 0.28 to < 0.43 mmol/L	< 0.67 mg/dL < 0.6 mEq/L < 0.28 mmol/L
Hypophosphatemia Adult and Pediatric > 14 Years	2.0 to < LLN mg/dL 0.63 to < LLN mmol/L	1.5 to < 2.0 mg/dL 0.47 to < 0.63 mmol/L	1.0 to < 1.5 mg/dL 0.31 to < 0.47 mmol/L	< 1.0 mg/dL < 0.31 mmol/L
Pediatric 1 Year–14 Years	3.0 to <LLN mg/dL 0.96 to <LLN mmol/L	2.5 to < 3.0 mg/dL 0.80 to < 0.96 mmol/L	1.5 to < 2.5 mg/dL 0.47 to < 0.80 mmol/L	< 1.5 mg/dL < 0.47 mmol/L
Pediatric < 1 Year	3.5 to <LLN mg/dL 1.12 to <LLN mmol/L	2.5 to < 3.5 mg/dL 0.80 to < 1.12 mmol/L	1.5 to < 2.5 mg/dL 0.47 to < 0.80 mmol/L	< 1.5 mg/dL < 0.47 mmol/L
Hyperbilirubinemia Adult and Pediatric > 14 Days	> 1.0 to 1.5 × ULN	> 1.5 to 2.5 × ULN	> 2.5 to 5.0 × ULN	> 5.0 × ULN
Infant, ≤ 14 Days (non-hemolytic)	NA	20.0 to 25.0 mg/dL 342 to 428 μmol/L	> 25.0 to 30.0 mg/dL > 428 to 513 μmol/L	> 30.0 mg/dL > 513 μmol/L
Infant, ≤ 14 Days (hemolytic)	NA	NA	20.0 to 25.0 mg/dL 342 to 428 μmol/L	> 25.0 mg/dL > 428 μmol/L
Blood Urea Nitrogen	1.25 to 2.50 × ULN	> 2.50 to 5.00 × ULN	> 5.00 to 10.00 × ULN	> 10.00 × ULN

CHEMISTRY				
	Grade 1	Grade 2	Grade 3	Grade 4
Hyperuricemia	>ULN to 10.0 mg/dL >ULN to 597 µmol/L	> 10.0 to 12.0 mg/dL > 597 to 716 µmol/L	> 12.0 to 15.0 mg/dL > 716 to 895 µmol/L	> 15.0 mg/dL > 895 µmol/L

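### Treatment-emergent laboratory counts cannot register further bilirubin or albumin worsening in subjects already at the top grade predose, and no SAP incidence table is relative to the subject's own baseline

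*SAP*

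**What the plan says.** Protocol 8.1.3 makes laboratory abnormalities part of the secondary endpoints: "The secondary endpoints are the incidences of AEs and laboratory abnormalities". Protocol 8.6.3 prespecifies graded treatment-emergent abnormalities by hepatic function group.

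SAP 7.2.2 applies the sponsor's grading scale, which "will be used to assign toxicity grades (0 to 4) to laboratory results for analysis". SAP 7.2.2.1 counts as treatment-emergent "values that increase at least 1 toxicity grade from predose at any postdose visit". It adds a second route: "If the relevant predose laboratory value is missing, any abnormality of at least Grade 1 observed within the time frame specified above" also counts. SAP 7.2.2.2 then places each subject by the worst postdose grade.

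In Protocol Appendix 4, adult bilirubin Grade 3 is "> 2.5 to 5.0 × ULN", and Grade 4 is everything above it. Adult albumin stops at Grade 3, below 2.0 g/dL. Protocol 7.5 describes the scale as "modified to be more appropriate for healthy volunteers and patients with inflammatory diseases"; hepatic impairment is not named.

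Protocol 4.2.2, criterion 14 ("Must meet all of the following laboratory parameters at Screening"), limits ALT, AST, neutrophils, platelets, hemoglobin and alpha-fetoprotein. It sets no limit on bilirubin or albumin.

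Protocol 7.7 uses multiples of ULN for controls. For impaired subjects it uses multiples of baseline: ALT or AST above 3 times baseline, or "ALT > 2 x baseline and total bilirubin > 2 x baseline".

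**The concern.** Impaired subjects can start part of the way up the bilirubin and albumin scales, or at the top. From the top there is no higher grade to reach, so the incidence count cannot respond. Just below a cut-point, a trivial change is counted. What the table shows then depends partly on where subjects start, and starting position differs by hepatic function group. With 10 subjects per group, one subject moves the incidence by 1/10 = 10 percentage points (1/8 = 12.5 points with 8).

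The protocol already treats baseline as the relevant reference for impaired subjects in 7.7. A subject could meet the full per-subject condition there and have no treatment-emergent entry for either test involved.

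**Working it through.** The plan gives no operating figure for this counting rule, so there is none to reproduce.

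**1. Rule applied to pairs of values.** Bilirubin cut-points from Appendix 4 are 1.0, 1.5, 2.5 and 5.0 x ULN.

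| Predose to postdose (x ULN) | Fold | Grade | Treatment-emergent? |
|---|---|---|---|
| 5.1 to 15.3 | 3.00 | 4 to 4 | No |
| 8 to 16 | 2.00 | 4 to 4 | No |
| 2.6 to 5.0 | 1.92 | 3 to 3 | No |
| 4.9 to 5.1 | 1.04 | 3 to 4 | Yes |
| 2.45 to 2.55 | 1.04 | 2 to 3 | Yes |

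**2. The full 7.7 condition with no graded entry.** ALT 0.6 to 1.24 x ULN is 1.24/0.6 = 2.07-fold and stays Grade 0, since Grade 1 starts at 1.25 x ULN. Bilirubin 5.1 to 10.3 x ULN is 10.3/5.1 = 2.02-fold and stays Grade 4. Both exceed 2 x baseline, and neither is treatment-emergent.

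**3. Share at the bilirubin ceiling (assumed distribution).** The documents give no bilirubin distribution. With a log-normal of median m and log-SD s, the share above 5 x ULN is 1 - Φ(ln(5/m)/s).
- m = 2, s = 0.5: ln(2.5)/0.5 = 1.83, giving 3%.
- m = 4, s = 0.7: ln(1.25)/0.7 = 0.32, giving 38%.

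**4. Noise in a stable subject (assumed log-normal within-subject CV).** There is one predose value and two scheduled postdose values (Day 5 and follow-up). If the true value sits on a cut-point, the chance of a false count is P(predose below) x P(at least one postdose above) = 1/2 x 3/4 = 37.5%, almost regardless of CV. Simulated chances elsewhere:

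| True value | CV 5% | CV 10% | CV 15% | CV 25% |
|---|---|---|---|---|
| 4.5 x ULN | 3% | 23% | 32% | 38% |
| 3.5 x ULN (mid-band) | 0% | 0.1% | 3% | 20% |

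For whole groups I took CV 15%, severe-group log-SD 0.6 and medians 2 to 4 x ULN. Noise alone then gives a treatment-emergent bilirubin grade in 16% to 22% of severe subjects. Controls (median 0.5 x ULN, log-SD 0.3 to 0.5, predose within normal) give 2% to 5%.

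**5. Grade rule against bilirubin > 2 x predose, for a true rise.** Same severe-group assumptions; medians 2 / 3 / 4 x ULN.

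| True rise | Grade rule | > 2 x predose | Either |
|---|---|---|---|
| 1.5-fold | 72 / 62 / 51% | 15% | 72 / 64 / 54% |
| 2-fold | 89 / 77 / 62% | 67% | 93 / 88 / 84% |
| 2.5-fold | 93 / 79 / 64% | 94% | 99 / 98 / 97% |

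With no true change, the fold rule flags 0.1% at CV 15% and about 4% at CV 25%. Neither rule dominates. The grade rule is better for moderate rises, and the fold rule is better for large rises from a high start.

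**The case against.** The strongest reply is that the SAP does what the protocol asks. Protocol 8.6.3 prespecifies graded treatment-emergent abnormalities, and Section 7.7 governs suspension of dosing, not tabulation. A reader might infer a protocol-SAP contradiction; there is none.

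A reader might also infer that worsening cannot be counted in severely impaired subjects generally, or across the liver tests. The documents do not support that. The bilirubin ceiling binds only subjects already above 5 x ULN; those at Grades 0 to 3 can still be counted. Entry at ALT and AST of at most 10 x ULN means none is at Grade 4 (above 10 x ULN) at Screening. ALT bands are two-fold wide, so any rise above 2-fold from a start between 0.625 and 10 x ULN moves at least one grade. Most subjects meeting the ALT-plus-bilirubin condition would therefore appear in the ALT row. Hemoglobin grades include a fall from baseline, and several other tests use absolute cut-points.

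Nor is worsening hidden. SAP 7.2.1 summarizes change from predose with its minimum and maximum, SAP 7.2 lists and flags individual results, and Protocol 7.5 makes abnormalities needing intervention or accompanied by signs or symptoms AEs. No formal testing is planned. Noise at a cut-point affects any graded count.

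All of this stands, and it limits the point. It does not supply a count: a group maximum shows the most extreme subject, and a listing shows values, but neither says how many subjects worsened relative to their own start. Noise at cut-points is likelier in impaired subjects because they can start within the graded range.

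**Conclusion.** The point holds for a defined subset. A subject with predose bilirubin above 5 x ULN or albumin below 2.0 g/dL cannot be counted as worsening on that test. The entry criteria admit such subjects, and no SAP incidence table is baseline-relative. This follows from the documents alone.

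How often it will matter is not in the documents. The 3% to 38% ceiling share, the false-count rates and the detection rates all rest on assumed bilirubin distributions and within-subject variability.

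A reader might conclude that a fold-change rule should replace the graded one. The calculation argues against that: for a true 1.5-fold rise the fold rule flags 15%, against 51% to 72% for the grade rule. ALT going from 4 to 11 x ULN (2.75-fold, Grade 2 to 4) is counted now, but would meet neither 7.7 multiple unless bilirubin also more than doubled. The supported conclusion is to add to the graded analysis. This is a cheap improvement to a descriptive safety summary.

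**What to change.** Keep the graded tables as the prespecified analysis. In SAP 7.2.2.2, add one supplementary table by hepatic function group within cohort, with the SAP 3.7.1 predose value as baseline, giving the number and percentage of subjects with:

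- ALT and/or AST > 3 x predose;
- ALT > 2 x predose together with total bilirubin > 2 x predose;
- total bilirubin > 2 x predose alone, labelled as a new descriptive category, because 7.7 uses that multiple only jointly with ALT.

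State that the first two take their multiples from Protocol 7.7 for tabulation only. Footnote the graded table with the number of subjects at the top grade at predose for each test. State that the two tables are read together, because the fold-change count is less sensitive to moderate rises.

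The cost is one more safety output from data already collected. No stopping or dosing rule changes.
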